2. LIST OF ABBREVIATIONS

Term	Definition / description
ADAs	Anti-drug antibodies
ADS	Analysis dataset
AE	Adverse event
AESI	Adverse event of special interest
ALT	Alanine aminotransferase
AST	Aspartate aminotransferase
ATC	Anatomical therapeutic chemical
BI	Boehringer Ingelheim
BIcMQ	Boehringer Ingelheim customized MedDRA Query
BMI	Body mass index
RPM	Report planning meeting
CARE	Clinical data analysis and reporting environment
CRF	Case report form
CTA	Clinical trial authorizations
CTP	Clinical trial protocol
CTR	Clinical trial report
DBLM	Database lock meeting
█	█
DMC	Data monitor committee
ECG	Electrocardiogram
eCRF	Electronic case report form
eDISH	Evaluation of drug-induced serious hepatotoxicity
EMA	European medicines agency
EOS	End of study
EOT	End of treatment
ES	Enrolled set
EudraCT	European union drug regulating authorities clinical trials
IB	Investigator's brochure
ICH	International council for harmonisation of technical requirements for pharmaceuticals for human use

Term	Definition / description
iPD	important protocol deviation
ISF	Investigator site file
LD	Day of last treatment received
MAA/BLA	Market Authorization Application/Biologics Licence Application
MACE	Major adverse cardiovascular event
MedDRA	Medical dictionary for regulatory activities
MQRM	Medical quality review meeting
Nab	Neutralizing antibody
NMSC	Non-melanoma skin cancer
NRI	No response imputation
OC	observed cases excluding values after any use of rescue medication or 6 weeks following last drug administration if patient early discontinued treatment
OC-IR	Observed cases including values after rescue therapy or treatment discontinuation
OLE	Open label extension
OR	Original results
PD	Protocol deviation
PGA	Physician global assessment
PK	Pharmacokinetic(s)
PRO	Patient-reported outcome
█	█
PT	Preferred Term
Q1	1 st quartile
Q3	3 rd quartile
RAGe	Report appendix generator
RCTC	Rheumatology common toxicity criteria
REP	Residual effect period
█	█
RPM	Report plan meeting
s.c.	subcutaneous
SAE	Serious adverse event

Term	Definition / description
SAF	Safety analysis set
SAF-MT	Safety analysis set for maintenance treatment
SAP	Statistical analysis plan
SAS TM	Statistical analysis software TM
SD	Standard deviation
SDL	Subject data listing
SI	Système international d'unités
SMQ	Standardised MedDRA query
SOC	System organ class
TB	Tuberculosis
TEAE	Treatment emergent adverse event
TS	Treated set
TS-MT	Treated set for maintenance treatment
TSAP	Trial statistical analysis plan
UDAEC	User-defined adverse event categories
ULN	Upper limit of normal range
█	█
WHO-DD	World health organisation – drug dictionary
WOCBP	Women of childbearing potential

3. INTRODUCTION

As per ICH E9 (1), the purpose of this document is to provide a more technical and detailed elaboration of the principal features of the analysis described in the clinical trial protocol (CTP) and its amendments, and to include detailed procedures for executing the statistical analysis of the primary and secondary variables and other data.

This trial statistical analysis plan (TSAP) assumes familiarity with the CTP and its amendments. In particular, the TSAP is based on the planned analysis specification as written in CTP Section 7 “Statistical Methods and Determination of Sample Size”. Therefore, TSAP readers may consult the CTP for more background information on the study, e.g., on study objectives, study design and population, treatments, definition of measurements and variables, and planning of sample size.

The statistical analyses will be performed within the validated working environment CARE, including SASTM (current Version 9.4, by [REDACTED]), and a number of SASTM-based tools (e.g., macros for the analyses of AE data or laboratory data; Report Appendix Generator system (RAGe) for compilation/formatting of the CTR appendices).

[REDACTED]

Since the primary aim of this study is to collect long-term safety and efficacy data on the use of Spesolimab (BI 655130) in patients with PPP who have completed their treatment in previous Spesolimab trials, multiple interim analyses will be done over the 5-year conduct phase of this trial in order to support, for example, regulatory interactions, Clinical Trial Authorizations (CTA), and MAA/BLA submissions, and also to provide important safety and efficacy information to the sponsor to guide further development of the compound, and to the investigators via IB updates and publications. Any data cut-off to be used for the reporting of trial data at interim will be presented in either a separate data cleaning plan, or in an appendix to this TSAP.

4. CHANGES IN THE PLANNED ANALYSIS OF THE STUDY

In the CTP, only one patient population will be analysed in this trial: the treated set for maintenance treatment (TS-MT). In the TSAP, the enrolled set (ES) is added for analysis of patient disposition, and the word “treated set” is changed to “safety analysis set (SAF)” for the consistency with other trials of the study compound.

[REDACTED]

- [REDACTED]
- [REDACTED]
- [REDACTED]
- [REDACTED]
- [REDACTED]

5. ENDPOINTS(S)

For the summary of all efficacy data, only those observations which were collected during the on-treatment period will be used.

For estimand and handling of missing data and the occurrence of inter-current events, unless otherwise specified, see [Section 6.3](#) and [Section 6.6](#).

Regarding the analyses of the change from baseline by visit or compared to baseline by visit for efficacy endpoints, unless otherwise specified, the baseline in parent trial is used, which refers to the last measurement collected prior to initiation of treatment in parent trials.

5.1 PRIMARY ENDPOINT(S)

The primary endpoint is the occurrence of treatment emergent adverse events (TEAEs) up to week 260 of maintenance treatment.

Please refer to [Section 7.8.1](#) for the description of the calculation of exposure-adjusted adverse event incidence rates.

5.2 SECONDARY ENDPOINT(S)

5.2.1 Key secondary endpoint(s)

[figure not shown]
Not applicable. No key secondary endpoints have been specified in the CTP.

5.2.2 Secondary endpoint(s)

Secondary endpoints are defined as described below. Note that for the secondary endpoints, any data collected after use of any rescue therapy or after 6 weeks following discontinuation of treatment (to allow for incorporation of the continuing maximum treatment effect period) in current trial are censored for the purpose of the primary estimand. This approach is in line with parent trial 1368.16.

- Percent change in PPP ASI from baseline in parent trial at week 48, 96, 144, 192, 240 and 260
- Proportion of patients with PPP ASI50 compared to baseline in parent trial at week 48, 96, 144, 192, 240 and 260
- Proportion of patients with PPP PGA of 0 (clear) or 1 (almost clear) at week 48, 96, 144, 192, 240 and 260

Derivations of PPP ASI related endpoints and PPP PGA related endpoints are described in [Section 10.1.1](#) and [Section 10.1.2](#).

5.4 OTHER VARIABLE(S)

5.4.1 Safety endpoints

Intensity of adverse events is assessed by Rheumatology Common Toxicity Criteria (RCTC) version 2.0.

Safety is assessed based on:

- Adverse events
- Safety laboratory values

Tests are listed in CTP Table 5.2.3: 1.

Lab tests are planned to be performed at the central laboratory service provider.

- Physical examination (documentation as baseline condition or AE)
- Vital signs, including
 - body temperature
 - pulse rate
 - systolic blood pressure
 - diastolic blood pressure
 - respiratory rate
- Relevant findings in 12-lead ECG (documentation as baseline condition or AE)
- Local tolerability

Local tolerability will be assessed by the investigator according to ‘swelling’, ‘induration’, ‘heat’, ‘redness’, ‘pain’, or other findings.
- ADA (anti-drug antibody), as detailed in the lab manual

5.4.2 Demographic and other baseline characteristics

Standard demographic data and baseline characteristics are used as recorded in the eCRF. These include sex, weight, height, BMI, race, ethnicity, age, site region and smoking history.

BMI will be calculated as weight [kg] / height [m]² (based on the last available weight measurement prior to the first dose of Spesolimab of extension trial).

Age [years] will be determined as the difference between year of birth and year of informed consent of current study.

Details of smoking history and changes for current extension trial will be summarized in an additional output based on treated patients.

Disease characteristics of PPP will describe time since first diagnosis [years] of PPP based on treated patients.

Disease characteristics of plaque psoriasis will describe time since first diagnosis [years]. Only treated patients who showed signs of chronic plaque psoriasis at baseline in parent trial will be included.

Time since first diagnosis/tonsillectomy [years] will be calculated as the difference between date of first diagnosis and date of informed consent of current study, divided by 365.25. For calculation in the context of incomplete information on the date of first diagnosis, cf. [Section 6.6.6](#).

5.4.4 Treatment compliance and treatment exposure

Treatment exposure will be assessed as the total dose of maintenance treatment [mg] administered. Per CTP Section 4.1.1, the investigational product is provided in prefilled syringes of either 1 mL or 2 mL (PFS-1 or PFS-2) volume, and the unit strength of the investigational product is 150 mg in 1 mL solution, the amount of Spesolimab within each syringe is 150 mg in 1mL prefilled syringe and 300 mg in 2 mL prefilled syringe. The total dose of maintenance treatment [mg] actually received will be calculated as the number of PFS-1 syringes actually injected multiplied by 150 mg plus the number of PFS-2 syringes actually injected multiplied by the 300 mg, which is:

Actual total dose [mg] =

Actual number of PFS-1 injected × 150 mg + Actual number of PFS-2 injected × 300 mg

The total duration of exposure will be calculated as the date of last administration of trial treatment minus the date of first administration of trial treatment + 1 day.

The treatment compliance per subject (as a % of planned) is defined as the actual total dose injected, divided by the total dose that patient should have received, times 100, which is

$$\begin{aligned} \text{Treatment compliance (\%)} &= \frac{\text{Actual total dose [mg]}}{\text{Planned total dose [mg]}} \\ &= \frac{\text{Actual number of PFS-1 injected} \times 150 \text{ mg} + \text{Actual number of PFS-2 injected} \times 300 \text{ mg}}{\text{number of planned visits} \times 600 \text{ mg}} \\ &\times 100. \end{aligned}$$

For the patients who discontinued the study treatment prematurely only the visits on or before premature discontinuation will be used for the calculation of overall compliance.

6. GENERAL ANALYSIS DEFINITIONS

6.1 TREATMENT(S)

The following maintenance treatment is planned in this study:

Spesolimab 600 mg q4w s.c. for up to 5 years for patients who have completed and clinically responded to the treatment with study drug (Spesolimab) in previous trials.

The following study phases are defined:

Table 6.1: 1 Flow chart of analysis phases of the study

Study analysis phase	Description	Start (included)	End (included)
Screening phase	Screening	Earliest of i) Date of informed consent, ii) First screening procedure	Date/time of start of injection for maintenance study drug minus 1 second
Maintenance treatment phase & Residual effect period	Maintenance on-treatment period	Date/time of start of injection of first maintenance study drug (Day 1 for maintenance)	Earliest of: i) Date of injection of last maintenance study drug + 112 days at 23:59, ii) cut-off for interim analysis if applicable.
Follow-up ¹ phase	Off-treatment period	Date of injection of last maintenance study drug + 113 days at 12:00 a.m.	Latest of: i) Date of EOS visit (Week 276 visit); ii) Last contact date on End of Study page at 11:59 p.m.

Dates are defined individually per patient. If more than one date is associated with a specific visit, measurements associated with a specific date are assigned to a study analysis phase according to the rules specified in the table. An analysis phase will not extend beyond the start date of the following phase.

¹ The follow-up phase only exists if the date of EOS visit or the last contact date is after the date of injection/infusion of last study drug + 112 days.

6.2 IMPORTANT PROTOCOL DEVIATIONS

Data discrepancies and deviations from the CTP will be identified for all patients in the database (i.e., enrolled patients). Consistency check listings (for identification of violations of time windows) and a list of protocol deviations will be provided to be discussed at the RPM/DBLM/MQRM. At this meeting, it will be decided whether a discrepant data value can be used in analyses or whether it must be queried in the clinical database. Each protocol deviation must be assessed to determine whether it is an important Protocol Deviation (iPD). For definition of iPDs, and for the process of identification of these, refer to the BI reference document "Identify and Manage Important Protocol Deviations (iPD)" (2).

If any iPDs are identified, they are to be summarised into categories and will be captured in the RPM/DBLM/MQRM minutes via an accompanying Excel spreadsheet (3). The following table contains the categories which are considered to be iPDs in this trial. If the data show other iPDs, for example, based on monitor visits to the sites, then this table will be supplemented accordingly by the time of the RPM/DBLM/MQRM. Not all iPDs will lead to

exclusion from analysis sets. IPDs leading to exclusion from analysis sets are indicated as such in [Table 6.2: 1](#).

As this is an open label, long term safety trial, all analyses will be performed based on the treated population only. Since no confirmatory efficacy testing is planned, no efficacy related iPDs leading to exclusion from analysis set are defined.

Table 6.2: 1 Important protocol deviations

Category/ Code	Description	Comments	Excluded from
A	Entrance criteria violated		
A1	Inclusion criteria not met		
A1.01	Have not completed treatment period in the parent trial LABEL: No completion of treatment period in parent trial	Inclusion criterion 2	None
A1.02	Have not obtained an individual health benefit, per investigator judgement (e.g. PPP PGA of 0 (clear) or 1 (almost clear) or other clinical improvement), from treatment in the parent trial LABEL: No individual health benefit from parent trial	Inclusion criterion 3	None
A1.03	Women of childbearing potential (WOCBP) who do not use highly effective methods of birth control per ICH M3 (R2) that result in a low failure rate of less than 1% per year when used consistently and correctly LABEL: Contraception methods not used for WOCBP	Inclusion criterion 4	None
A2	Exclusion criteria met		
A2.01	Be pregnant, nursing, or plan to become pregnant while in the trial LABEL: Pregnant or nursing	Exclusion criterion 1	None

Table 6.2: 1 Important protocol deviations (continued)

Category/ Code	Description	Comments	Excluded from
A2.02	Have experienced study treatment-limiting adverse events during parent trial LABEL: Treatment-limiting AE during parent trial	Exclusion criterion 2	None
A2.03	Congestive heart disease, as assess by the investigator LABEL: Congestive heart disease	Exclusion criterion 4	None
A2.04	Known history of lymphoproliferative disease LABEL: Lymphoproliferative disease	Exclusion criterion 6	None
A2.05	Any documented active or suspected malignancy or history of malignancy within 5 years prior to screening in parent trial, except appropriately treated basal cell carcinoma of the skin, squamous cell carcinoma of the skin or in situ carcinoma of uterine cervix LABEL: Malignancy	Exclusion criterion 7	None
A2.06	Have developed active or severe infective disease and opportunistic infections/infective diseases LABEL: Infective disease Exception: Patients with latent TB during preceding trial are allowed to be included in the extension study, provided they have received and/or receive currently appropriate treatment according to local guidelines.	Exclusion criterion 8	None
A2.07	Any restricted medication as specified in CTP or any drug considered by investigator likely to interfere with the safe conduct of the study since the last visit of parent trial and during screening period for current trial # LABEL: Restricted medication interfering safety	Exclusion criterion 9	None

Table 6.2: 1 Important protocol deviations (continued)

Category/ Code	Description	Comments	Excluded from
A2.08	History of allergy/hypersensitivity to a systemically administered trial medication agent or its excipients LABEL: Allergy/hypersensitivity to trial medication	Exclusion criterion 11	None
A2.09	Presence of acute demyelinating neuropathy LABEL: Acute demyelinating neuropathy	Exclusion criterion 18	None
B	Informed consent		
B1	Informed consent not available/not done LABEL: IC not available	Date of informed consent missing or no signature on patient's "Declaration of Informed Consent"	All analyses
B2	Informed consent too late LABEL: IC too late	Date of informed consent not obtained prior to any study related procedure. Minimum requirement for initial informed consent <= date of Visit 1/date of any study procedure; a late signature but subject was fully informed and gave their consent verbally before or a new informed consent version signed late but subject's rights, safety or wellbeing were not impacted. If this is documented later on and signed by the subject, such cases do not qualify as iPD.	None
C	Trial medication		
C1	Incorrect treatment medication dose received by patients LABEL: Incorrect medication dose administration	Treatment dose > 1200 mg within 4 weeks.	None

Table 6.2: 1 Important protocol deviations (continued)

Category/ Code	Description	Comments	Excluded from
D	Concomitant medication		
D1a	Use of not allowed medication or non-drug therapies as per protocol for other reason before last drug administration # LABEL: Restricted medication for other reason		None
D1b	Use of not allowed medication or non-drug therapies as per protocol for Covid-19 before last drug administration # LABEL: Restricted medication for Covid-19		None
D1c	Use of rescue medication and not discontinued from the trial treatment LABEL: Rescue medication and not trial treatment discontinuation		None
G	Pregnancy test		
G1	Pregnancy test not done for woman of childbearing potential per CTP flowchart # LABEL: Pregnancy test not done	Urine pregnancy test not done at any visit where such is scheduled, and serum pregnancy test not done when urine pregnancy test showed positive results.	None

PD will be detected manually;

6.3 SUBJECT SETS ANALYSED

The following analysis sets will be defined for this trial:

Enrolled set (ES)

This patient set includes all patients who signed informed consent. It will be used for display of patient disposition.

Safety analysis set for maintenance treatment (SAF-MT)

This patient set includes all patients who received at least one dose of the maintenance treatment. This set will be used for presentation of iPDs, patient listings, safety and efficacy during the maintenance part of the extension trial.

[Table 6.3: 1](#) illustrates the data sets which are to be used for each category class of endpoints, and the approaches used with regard to missing data. For explanation of the different methods of handling missing data, cf. [Section 6.6](#).

Table 6.3: 1 Subject sets analysed

Class of endpoint	Subject set	
	ES	SAF-MT
Disposition	OR	
Compliance and exposure		OR
iPD		OR
Baseline conditions/medical history		OR
Concomitant medications Concomitant non-drug therapies		OR
Demographics Baseline characteristics		OR
Primary endpoint		OR
Secondary endpoints		OC: for continuous efficacy endpoints OC-NRI: for binary efficacy endpoints
Further endpoints		OC: for continuous efficacy endpoints OC-NRI: for binary efficacy endpoints
AE		OR
Lab data, vital signs		OR OC-IR

NRI = Non Response Imputation, cf. [Section 6.6.2](#).

OC = observed cases excluding values after any use of rescue medication or 6 weeks following last drug administration if patient early discontinued treatment, OC-IR = observed cases including also values after any rescue medication or treatment discontinuation, OR = original results.

6.5 POOLING OF CENTRES

All patients from all centres will be pooled for descriptive analyses.

6.6 HANDLING OF MISSING DATA AND OUTLIERS

Section 7.3 of the CTP describes the handling of missing data.

The original results (OR) approach implies the presentation of data exactly as observed (not using time windows).

OR analysis will be performed on parameters and endpoints that are either not affected by patients' rescue therapy use (e.g. plasma concentration level of Spesolimab, rescue therapy use itself), or, if it is not meaningful to apply any imputation rule for the replacement of missing values.

6.6.1 Withdrawals

The reasons for withdrawal from treatment will be reported as indicated on the eCRF.

6.6.2 Efficacy data

Based on the different reasons for patients' data missing for different endpoints, various approaches will be used to assess the impact of missing data on the efficacy endpoints of this

trial, depending upon the type of the endpoint (cf. [Table 6.3: 1](#)). Approaches to be applied are described below.

Continuous efficacy endpoints

For efficacy endpoints which are continuous in nature, the following imputation strategy will be applied to display the continuous efficacy data.

- Observed cases (OC) approach will include all collected data, with no imputation performed on the missing data. Such an OC approach will exclude all values measured after intake of a rescue therapy or after 6 weeks following last drug administration if a patient discontinued treatment early.
- Observed cases including all observed data (OC-IR) will be used as a sensitivity method for data display and is an extension of the OC approach which includes additionally all values which were measured after rescue therapy or treatment discontinuation.

Binary efficacy endpoints

For all binary endpoints (i.e. endpoints that are either 1 (patient responded) or 0 (patient did not respond)), the following will be performed as the primary imputation approach (analysis type: No Response Imputation [NRI]):

- If there are data at visits both before and after the visit with a missing outcome, then impute as success only if both neighbouring visits also represent a success (independent of whether the preceding and following observations were selected for analysis based on time windows described in [Section 6.7](#) and no rescue treatment has been given during this period);
- Otherwise, impute as a failure to achieve a response;
- Only patients continuing at this visit per analysis time window will be included in the denominator, excluding also ongoing patients before achieving this visit due to interim cut-off.

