## Trial Design

[figure not shown]

Figure 3.1: 1 One single arm: Spesolimab (BI 655130) 600mg s.c. q4w over 260 weeks

For patients who terminate study drug prematurely in this extension study the subsequent visit will be replaced by an early EoT visit followed by an EoS visit 16 weeks after the last study drug administration (see Figure 3.1: 1).

Interim analyses of [REDACTED] and clinical data may be performed throughout the conduct phase of this 5-year study to support future trial applications, investigator brochures, regulatory documents and scientific publications. The final analysis of the entire trial data will be performed once all patients have completed the last scheduled trial visit. Individual patient participation is concluded when the patient has completed the last scheduled visit. The end of whole study is defined as “last patient out”; i.e. last scheduled visit completed by the last patient in the study.

An independent Data Monitoring Committee will evaluate safety and efficacy data on a continuous basis.

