#### 3.3.4.1 Wish to discontinue trial treatment, non-compliance of patient, medical reason and intake of restricted medication

An individual patient will be withdrawn from the trial if:

- The patient wants to discontinue trial treatment, without the need to justify the decision. This includes patients losing individual perceived health benefit or becoming aware of a preferred treatment option.
- The patient has repeatedly shown to be non-compliant with important trial procedures and, in the opinion of both, the investigator and sponsor representative, is not willing or able to adhere to the trial requirements in the future.
- The patient can no longer receive trial treatment for medical reasons (such as surgery, adverse events – see also [Section 3.3.4.3](#), other diseases, or pregnancy). The patient took restricted medication which is not allowed acc. to [Section 4.2.1](#) and [Table 4.2.1: 1](#).

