#### 3.3.4.2 Implications due to loss of treatment response

- Patients who need to take rescue medication must be discontinued from the trial. Rescue therapy is defined as the use of topical corticosteroids or other topical treatment, systemic immunomodulating treatments or biologics and therapy such as tonsillectomy, for the treatment of worsening of PPP. For the complete list and all details of restricted medication see [Section 4.2.1](#) and [Table 4.2.1: 1](#).
- The following additional trial treatment discontinuation criteria apply from Visit 2 onwards:
  - Increase of pustulation severity compared to baseline (baseline (V1) of extension trial)AND
  - Loss of PPP ASI by  $\geq 5$  points compared to baseline (baseline (V1) of extension trial)

A patient who meets the trial treatment discontinuation criteria at 2 consecutive visits must be discontinued from the trial treatment and administered standard of care therapy.

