Disposition of the patient population participating in the trial will be summarised by presentation of the frequency of patients enrolled, treated, enrolled but not treated, who completed all doses of trial medication as planned, who completed the trial (EOS), who were prematurely discontinued study treatment, by reason and who withdrew from the trial, by reason. The frequency of patients with iPDs will be presented; the iPDs will be listed per patient.

To better illustrate the long-term disposition of entire maintenance treatment (cf. [Section 6.1](#)), a summary table regarding patient status over time will be added. The cumulative frequency of patients for the following categories will be displayed based on 16-week intervals:

- Ongoing on study medication, i.e., without early treatment discontinuation by the time point
 - Intake of rescue medication
- Pre-maturely stopped study medication, i.e., discontinued study medication by the time point
 - Intake of rescue medication
 - Death
 - Any of the above
- Ongoing but not achieved the visit
 - Intake of rescue medication

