7.5.2 Secondary endpoints

Descriptive summaries and graphical displays (line plots) will be produced using OC method for continuous secondary endpoints and OC-NRI method for binary secondary endpoints respectively.

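### SAP 6.6.2 calls its primary binary method No Response Imputation but drops patients who stopped earlier from each visit's denominator, so an all-treated proportion should be shown beside the planned one

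*SAP*

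**What the plan says.** The two binary secondary endpoints are the proportions of patients with PPP ASI50 and with PPP PGA 0 or 1 at weeks 48, 96, 144, 192, 240 and 260 (Protocol 2.1.3, SAP 5.2.2). Neither definition names a denominator. The efficacy analysis set is SAF-MT, all patients with at least one maintenance dose (SAP 6.3).

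SAP 6.6.2 sets the primary approach for binary endpoints and calls it No Response Imputation. A missing outcome becomes a success only if both neighbouring visits are successes, and otherwise a failure. The third bullet then restricts who is counted: "Only patients continuing at this visit per analysis time window will be included in the denominator". It also leaves out ongoing patients who have not reached the visit at an interim cut-off.

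Table 6.3: 1 lists "OC-NRI: for binary efficacy endpoints", and SAP 7.5.2 plans summaries and line plots by the "OC-NRI method for binary secondary endpoints respectively". The sensitivity display that includes data after rescue or discontinuation (OC-IR) is described for continuous efficacy endpoints only.

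The protocol ties some exits to outcome:

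- Section 3.3.4.2, on rescue: "Patients who need to take rescue medication must be discontinued from the trial".
- Section 3.3.4.2, on worsening against the extension baseline: "A patient who meets the trial treatment discontinuation criteria at 2 consecutive visits must be discontinued from the trial treatment".
- Section 3.3.4.1, on a patient's wish to stop: "This includes patients losing individual perceived health benefit or becoming aware of a preferred treatment option".

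**The concern.** A reader who sees a non-response imputation label will assume that dropouts were counted as failures. Here they leave the calculation. A rescue user taken off treatment as the protocol requires disappears from later denominators. A rescue user kept on treatment in breach of the protocol (deviation D1c in SAP Table 6.2: 1) stays in, normally as an imputed failure.

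The planned proportion answers the question: of those still on treatment, how many respond? Because exit is partly related to outcome, that can differ widely from response among everyone treated, and the gap widens over five years. Interim results are meant to support regulatory submissions, investigator brochure updates and publications (Protocol 7.2.7, SAP 3), so the label and the denominator will be read by people who do not have the SAP to hand.

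A second gap is that the SAP does not define when a patient is continuing at a visit, so two programmers could produce different counts.

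**Working it through.** The plan has no figure to reproduce. The trial is descriptive, there is no sample size calculation, and the 500 patients are an expected roll-over number (Protocol 7.1, 7.5). Every stopping, switching and response rate below is an assumption.

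**1. Does another rule restore the full denominator?** The general remarks in SAP 7 base percentages on all patients in the set, but only where nothing more specific is stated. The third bullet of 6.6.2 is more specific and prevails.

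**2. Relation between the two proportions.** With patients who stopped counted as non-responders:

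all-treated proportion = planned proportion × (n continuing / N who reached the visit)

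For a constant yearly stopping rate *a*, the fraction continuing at week *w* is (1 − *a*)^(*w*/52.18), so the planned figure exceeds the all-treated figure by the factor (1 − *a*)^(−*w*/52.18).

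| Assumed yearly stopping | Factor, wk 48 | Factor, wk 96 | Factor, wk 260 | All-treated if planned is 70%, wk 48 | Same, wk 260 | Continuing of 500, wk 260 |
|---|---|---|---|---|---|---|
| 10% | 1.10 | 1.21 | 1.69 | 63.5% | 41.4% | 296 |
| 20% | 1.23 | 1.51 | 3.04 | 57.0% | 23.0% | 164 |
| 30% | 1.39 | 1.93 | 5.91 | 50.4% | 11.8% | 85 |

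**3. Selective exit alone can raise the planned figure.** Take 500 treated patients, 200 of them sustained responders, with only non-responders leaving. After 0, 100, 200 and 250 exits the planned proportion is 200/500 = 40.0%, 200/400 = 50.0%, 200/300 = 66.7% and 200/250 = 80.0%. The all-treated proportion stays at 40.0%, and nobody has improved.

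**4. A less extreme model.** Start with 60% responders. In each 16-week step, 2% of both groups leave for other reasons. Then 5% of responders lose response and stay as counted failures, 5% of non-responders gain response, and a share *q* of non-responders leave.

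| *q* per 16 weeks | Planned, wk 48 → wk 240 | All-treated, wk 48 → wk 240 |
|---|---|---|
| 10% | 63.8% → 69.6% | 53.4% → 30.7% |
| 5% | 60.5% → 61.5% | 53.7% → 33.8% |
| 2% | 58.6% → 55.9% | 53.8% → 36.4% |

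The planned figure can rise, hold or fall. The all-treated share falls in all three cases.

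**5. Who is continuing?** Protocol 3.1 says that after premature termination "the subsequent visit will be replaced by an early EoT visit". Suppose the last dose is at week 44 (Day 309) and the early EoT visit is on Day 337.

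- The extended week 48 window is Days 282 to 393 (SAP Table 6.7: 2), so the value falls inside it.
- The six-week limit is Day 309 + 42 = Day 351, so the value is not censored.

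The patient has a usable week 48 value but has stopped treatment. The SAP does not say whether that patient is in the week 48 denominator.

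**The case against.** The strongest reply is that this is an openly stated choice. The denominator appears in the same three-bullet rule as the imputation, and it suits the plan's on-treatment focus: SAP 5 limits efficacy summaries to on-treatment observations, and SAP 5.2.2 censors data after rescue, or more than six weeks after discontinuation, for the primary estimand. That is a good reason to keep the planned proportion. It does not justify the label. Those sections censor data; they do not take patients out of the proportion.

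Readers can also rebuild much of the missing figure. SAP 7 requires counts as well as percentages, and its disposition table reports, by 16-week interval, patients in the category "Pre-maturely stopped study medication, i.e., discontinued study medication by the time point" as well as those ongoing. Five of the six endpoint visits are multiples of 16 weeks; week 260 is not. This mitigates the problem, but the efficacy tables and line plots would still not print the figure.

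The link between exit and response is loose. Worsening is judged against the extension baseline and ASI50 against the parent baseline, so a patient can be forced off while still an ASI50 responder. PPP ASI is scheduled only every 16 weeks, so a worsening patient will usually contribute observed values before leaving. Stable non-responders may stay, and patients also leave for surgery, pregnancy or other diseases. All of this stands, and it is why the direction of drift is uncertain and both proportions are needed.

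Parts of the SAP are redacted, so a companion display may exist there. The readable sections that govern these endpoints (6.3, 6.6.2, 7.5.2) show none. Finally, nothing is tested, the primary endpoint is safety, and Protocol 3.2 accepts selection bias in general. The effect is therefore on interpretation and not on error rates; Protocol 3.2 does not address this denominator.

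**Conclusion.** The concern holds and should be fixed. Under SAP 6.6.2 the PPP ASI50 and PPP PGA 0/1 proportions describe patients still continuing at each visit, while the method's name implies that dropouts count as failures. The size depends on the unknown stopping rate. For 10% to 30% a year the planned figure would be 1.10 to 1.39 times the all-treated figure at week 48, and 1.69 to 5.91 times at week 260. These factors measure the distance between two different quantities, not a proven bias, and they rest on constant exit rates and on counting every patient who stopped as a non-responder. The text of the rule and the gap in the definition of continuing depend on no assumption. The absence of a companion figure is established only for the readable text.

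**What to change.** Amend SAP 6.6.2, Table 6.3: 1 and 7.5.2 as follows:

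1. Keep the planned proportion, relabel it as the proportion among patients continuing on treatment, and print the number continuing at each visit.
2. Define continuing, and state whether a patient with an uncensored early EoT value inside the visit window belongs to that visit's denominator.
3. For PPP ASI50 and PPP PGA 0/1, add a proportion over all SAF-MT patients whose first maintenance dose was early enough to reach the visit by the data cut-off. Apply that test equally to discontinued and ongoing patients, and treat a sponsor-wide stop as a cut-off. Count discontinuation or rescue before the visit as non-response.
4. Show the two proportions side by side with the number who reached the visit, the number continuing, and the reasons for stopping already reported under SAP 6.6.1.

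The cost is SAP wording, one denominator flag and one extra column or line per endpoint, from data already held. No trial procedure changes. The drawback is that the added rates will look less favourable and will count exits unrelated to response as failures, which is the reason for showing both.
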